11.0 Recruitment Methods

N/A: This is a records review only, and subjects will not be recruited. NOTE: If you select this option, please make sure that

all records review procedures and inclusion/exclusion screening are adequately described in other sections.

11.1 Describe when, where, and how potential subjects will be recruited.

NOTE: Recruitment refers to how you are identifying potential participants and introducing them to the study. Include specific methods you will use (e.g. searching charts for specific ICD code numbers, Research Participant Groups, posted advertisements, etc.).

Response:

It is anticipated that patients with COVID-19 will call their primary care physicians or present to emergency rooms. Recruitment efforts will include dissemination of information about this trial to these health care providers. We will be sending a flyer for recruitment (submitted) to primary care practices, emergency rooms and urgent care centers in the area, such as UBMD primary care practices and Kaleida and ECMC emergency rooms. The health care practitioners will provide potential participants the contact information for study staff. Only potential participants who then contact the study staff will be enrolled in this study.

We will be working with the Clinical and Translational Science Institute (CTSI) Community Engagement Team (CET) to create awareness of the study through their professional and community contacts. The tools they have available may include the Buffalo Research Registry (BRR, IRB Approved STUDY00000806), the Patient Voices Network (PVN), the Conventus CTSI/PVN and Evergreen Research Tables, and conducting outreach at various community events. These tools are methods by which the CET distributes IRB-approved recruitment information to community members.

We will also utilize the services of The CTSI Community Engagement Team (CET) to assist in participant recruitment.

BUFFALO RESEARCH REGISTRY

The Clinical and Translational Science Institute's (CTSI) Community Engagement Team (CET) hosts the Buffalo Research Registry (BRR, IRB Approved STUDY00000806), a resource that connects researchers looking to recruit participants and community members looking to get involved with research. To participate in the registry, volunteers complete a voluntary intake form.

Volunteers have agreed to be contacted about potential research opportunities based on their self-reported information.

As described in the BRR's IRB Approved Protocol (STUDY00000806), key personnel from the CTSI will serve as the conduit between our research team and the registry volunteers. Key personnel will verify our IRB study approval, review inclusion and exclusion criteria and will sort the registry data accordingly.

In terms of recruiting for our study, key personnel will pull volunteer reports using the inclusion and exclusion criteria. Key personnel will centrally invite volunteers to participate in the study and provide a warm hand off to our team.

There are two ways we may share our study. These include:

1. Electronically- Using the volunteer report from REDCap, key personnel from the CTSI will send initial e-mail invites to introduce our study to registry volunteers.
2. Post Mail- Key personnel from the CTSI will provide our team with contact information (i.e. first name, last name, post mail address) to prepare a mailing. This information will be shared in a password protected excel spread sheet. The password to the spreadsheet will be sent in a separate follow-up e-mail.

We will only use the list for this protocol and we agree to destroy the list once recruitment for the study has closed. We also plan on conducting follow-up by phone/email after initial contact. This contact information will be provided in a password protected excel spread sheet. The password to the spreadsheet will be sent in a separate follow-up e-mail. We will only use the list for this protocol and we agree to destroy the list once recruitment for the study has closed. We will have no access to the health information provided in the registry.

The CET hosts the Buffalo Research Registry (BRR, IRB Approved STUDY00000806), a voluntary registry which can connect us to community members who have completed a health profile and are interested in participating in research. These community members have agreed to be contacted about potential research opportunities based on their self-reported information.

COMMUNITY OUTREACH AND TABLING

The CET also tables at many events in the community throughout the year and may display the IRB approved flyer for this project at their table at community events. Examples of events the CET attends include Good for the Neighborhood hosted by Independent Health Foundation, UB on the Green, Juneteenth, Elmwood Arts Festival and many others.

The CET also hosts standing tables at the Conventus Building on the 4th floor of UBMD and at Evergreen where the IRB approved flyer can be made available to community members and patients. This will occur only after agreement between the CET and UBMD Conventus and/or Evergreen partners that the study is appropriate for the venue.

Social Media Recruitment Plan

This study will be shared via the social media platform Facebook. At this time no paid ads will be placed. A member of the study team member will contact social media managers and group/page administrators to request they post our Facebook post content to their public Facebook pages or private groups.

11.2 Describe how you will protect the privacy interests of prospective subjects during the recruitment process.

NOTE: Privacy refers to an individual's right to control access to him or herself.

Response: Prospective subjects control their own privacy interests as they will contact the research team if interested in participation. Prospective subjects will be interviewed over the phone where the interviewer will be in a private room.

11.3 Identify any materials that will be used to recruit subjects.

NOTE: Examples include scripts for telephone calls, in person announcements / presentations, email invitations.

 For advertisements, include the final copy of printed advertisements with your submission. When advertisements are taped for broadcast, attach the final audio/video tape. NOTE: You may submit the wording of the advertisement prior to taping to ensure there will be no IRB-required revisions, provided the IRB also reviews and approves the final version.

Response: We will be sending a flyer for recruitment to primary care practices, emergency rooms and urgent care centers in the area. The same flyer will be posted on social media. A telephone script will be used when the participant calls the research team to introduce the study. Both are submitted.

12.0 Procedures Involved*

12.1 Provide a description of *all research procedures or activities* being performed and when they are performed once a subject is screened and determined to be eligible. Provide as much detail as possible.

NOTE: This should serve as a blueprint for your study and include enough detail so that another investigator could pick up your protocol and replicate the research. For studies that have multiple or complex visits or procedures, consider the addition of a schedule of events table in in your response.

Response: Because of the highly contagious nature of COVID infection in the first few days after onset of symptoms, it is essential to minimize exposure of research team members to the subjects. Therefore, except for the enrollment visit, all procedures for this study will be conducted remotely at the subject's home. The Table below depicts all the research procedures.

	Screen	Enrollment							
Day +/- Window	-1 or 1	1	Daily until	Daily until	Day 3 ± 1	Day 7 ± 1	Day 14 ± 2	Day 28 ± 3	Day 42 ± 3

			day 14	day 42					
Assessments/Procedures									
ELIGIBILITY									
Informed consent	X								
Demographics & Medical History	X								
Prior SARS-CoV-2 based on screening or perform rapid antigen testing	X								
STUDY INTERVENTION									
Randomization		X							
Administration of Melatonin/Placebo		X	X						
STUDY PROCEDURES									
Body temperature		X	X	X	X	X	X	X	X
Clinical data collection		X	X	X	X	X	X	X	X
Pulse Oximetry measurement		X	X	X	X	X	X	X	X
Adverse event evaluation		X			X	X	X	X	X
RESEARCH LABORATORY									
Saliva for PCR SARS-CoV-2		X			X	X	X	X	X
Saliva for Cytokine/Chemokine RNA and/or protein		X			X	X	X	X	X

Below is a day by day description of the study procedures.

- For those subjects that have not had a COVID-test: Subjects will be enrolled and then tested for SARS-CoV2 using an EUA rapid antigen administered by the study team. If negative by rapid antigen test subjects will be withdrawn from study. Those subjects that have a prior positive test will not be give a rapid antigen test.
- If COVID-19 positive:
- Collect a baseline sample of saliva prior to taking drug, by spitting in a collection container that will be provided at time of consent.
- Rate COVID symptoms before starting medication and then each day in the evening on a short questionnaire from Day 1 to Day 42.
- Record body temperature and pulse oximetry each day in the morning and evening.
- Take the IP 3 times a day orally for 14 days.
- On Days 3, 7, 14, 28 and 42 collect a sample of saliva prior to taking drug in a collection container provided. Place the sample in a collection bag and place it in a freezer.
- Speak to the research coordinator through telemedicine on Days 3, 7, 14, 28 and 42 to provide

data as well as any adverse effects of the treatment. These include anxiety and depression and drowsiness special interest adverse events. The duration of these visits will be 15-30 minutes.

- Allow a courier to come to your house to collect study related materials on Day 15 ± 3 and day 43 ± 3 to pick up study related materials.

12.2 Describe what data will be collected.

NOTE: For studies with multiple data collection points or long-term follow up, consider the addition of a schedule or table in your response.

Response: Please see Table above

12.3 List any instruments or measurement tools used to collect data (e.g. questionnaire, interview guide, validated instrument, data collection form).

Include copies of these documents with your submission.

Response: Included documents: 1) Data collection form (baseline); 2) Data collection form (Follow-up); 3) Daily symptom questionnaire; 4) Body temperature and pulse oximetry logs; 5) Instructions for saliva collection, storage and shipping 6) WHO Clinical Progression Scale

12.4 Describe any source records that will be used to collect data about subjects (e.g. school records, electronic medical records).

Response: EMR data will be accessed to ascertain baseline health information and information relevant to the participants COVID illness. The study team will have remote access to the relevant EMRs.

12.5 Indicate whether or not **individual** subject results, such as results of investigational diagnostic tests, genetic tests, or incidental findings will be shared with subjects or others (e.g., the subject's primary care physician) and if so, describe how these will be shared.

Response: No

12.6 Indicate whether or not **study** results will be shared with subjects or others, and if so, describe how these will be shared.

Response: Study results will be posted on Clinical Trials.gov and submitted for publication in a peer reviewed journal.

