3.0 Scientific Endpoints*

2.1 Describe the scientific endpoint(s), the main result or occurrence under study.

*NOTE: Scientific endpoints are outcomes defined before the study begins to determine whether the objectives of the study have been met and to draw conclusions from the data. Include primary and secondary endpoints. Some example endpoints are: reduction of symptoms, improvement in quality of life, or survival. Your response should **not** be a date.*

Response:

Primary Objective

Evaluate the safety of the intervention through 42 days of follow-up as compared to the control arm as assessed by:

- Cumulative incidence of serious adverse events (SAEs)
- Cumulative incidence of Grade 3 and 4 adverse events (AEs).

- Adverse Events of Special Interest
- Discontinuation or temporary suspension of the investigational medication (for any reason).

Secondary Objectives

Evaluate the clinical efficacy of melatonin as compared to placebo as assessed by:

Hospitalization: Incidence of COVID related hospitalization at 42 days.

Data will be obtained from electronic medical record.

COVID related symptoms: Fever, chills, cough, nasal symptoms, body aches/muscle aches, headache, loss of smell, loss of taste, nausea, vomiting, diarrhea, fatigue, dizziness. The speed of resolution of COVID related symptoms. Change from baseline, Day 1 to Day 42. Accessed by questionnarre.

Change in the WHO Clinical Progression Scale (0-10). Data will be obtained from electronic medical record.

Mortality: 42-day mortality. Data will be obtained from electronic medical record.

Exploratory Objective

Evaluate the effect of melatonin on virologic parameters as compared to placebo and assessed by:

-Percent of subjects with SARS-CoV-2 detectable in saliva sample at days 1, 3, 7, 14, 28 and 42.

-Quantitative RT-PCR for SARS-CoV-2 virus in saliva sample at days 1, 3, 7, 14, 28 and 42.

-Evaluate the reduction in cytokine/chemokine RNA and/or protein levels in saliva:

-Reduction as compared to baseline (Day 1) in salivary levels of cytokine/chemokine RNA and/or protein (IL-1, IL-2, IL-3, IL-4, IL-6, IL-8, IL-10, IL-11, IL-12, IL-13, IL-17, IL-18, TNF α , IFNy, IFN α , IFN-B, MCP1) at days 3, 7, 14, and 28.

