21.0 Provisions to Monitor the Data to Ensure the Safety of Subjects*

N/A: This study is not enrolling subjects, or is limited to records review procedures only. This section does not apply.

NOTE: Minimal risk studies may be required to monitor subject safety if the research procedures include procedures that present unique risks to subjects that require monitoring. Some examples include: exercising to exertion, or instruments that elicit suicidality or substance abuse behavior. In such cases, N/A is not an acceptable response.

21.1 Describe the plan to periodically evaluate the data collected regarding both harms and benefits to determine whether subjects remain safe.

Response: On a weekly basis the co-PIs will review the data being collected to determine if there are any worrisome patterns of the adverse events (grade 3 or 4) and SAEs reported. This review will be blinded. We do anticipate a 20% rate of hospitalization in our subjects. Therefore, only if the rate is much higher than that will there be a cause of concern.

21.2 Describe what data are reviewed, including safety data, untoward events, and efficacy data.

Response: All safety data will be reviewed.

External Review of Data

[name], an infectious disease specialist at University of Buffalo will serve as an external reviewer for the outcomes collected in this study. Specifically, he will adjudicate whether the adverse events (grade 3 or 4) and SAEs collected are drug or disease related. He will also adjudicate whether the hospitalizations observed in this study were COVID related or not. These adjudications will be on blinded data.

21.3 Describe any safety endpoints.

- Response: Cumulative incidence of serious adverse events (SAEs)
 - Cumulative incidence of Grade 3 and 4 adverse events (AEs).
 - Adverse effects of special interest: Anxiety and Depression (GAD-2 and PHQ-2 questionnaires); Drowsiness (will be recorded)
 - Discontinuation or temporary suspension of the investigational medication (for any reason).

21.4 Describe how the safety information will be collected (e.g., with case report forms, at study visits, by telephone calls with participants).

Response: The safety information will be collected by scheduled phone calls as described above.

21.5 Describe the frequency of safety data collection.

Response: Days 1, 3, 7, 14, 28 and 42

21.6 Describe who will review the safety data.

Response: The co-PIs will review the data along with the biostatistician [name].

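### Section 12.1 words the safety calls in causal terms, which conflicts with endpoints that carry no relatedness condition and could under-capture events not blamed on the drug

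*Combined protocol and SAP*

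**What the plan says.** Section 12.1 lists what happens day by day. On Days 3, 7, 14, 28 and 42 the subject speaks to the coordinator by telemedicine and provides "data as well as any adverse effects of the treatment". The next sentence reads "These include anxiety and depression and drowsiness special interest adverse events". In the schedule table of the same section, the matching row is simply "Adverse event evaluation".

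Section 21.4 says of the route: "The safety information will be collected by scheduled phone calls as described above". Section 21.5 gives the times as "Days 1, 3, 7, 14, 28 and 42".

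Section 3.0 lists among the primary safety measures "Cumulative incidence of serious adverse events (SAEs") and "Cumulative incidence of Grade 3 and 4 adverse events (AEs"). Neither is limited to events related to treatment, and sections 1.0, 19.1 and 21.3 add no such limit. On cause, section 21.2 says of the blinded external reviewer: "he will adjudicate whether the adverse events (grade 3 or 4) and SAEs collected are drug or disease related".

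Section 3.0 takes COVID-related hospitalization, the WHO scale and mortality from the electronic medical record (EMR). Section 12.4 confines EMR use to baseline health and the COVID illness.

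**The concern.** The call wording places a judgement of cause at the point of collection, whereas the plan elsewhere reserves that judgement for a blinded reviewer. That reviewer can only consider what was collected. An event that the subject or coordinator puts down to COVID, or to something unrelated, may never be recorded, and would then also be absent from the weekly review in section 21.1.

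Subjects are poorly placed to make the attribution. Headache, nausea and dizziness appear both among the COVID symptoms in section 3.0 and among the melatonin risks in section 23.1. Treatment lasts 14 days, so the Day 28 and Day 42 calls fall about two and four weeks after it ends, when a question about treatment effects may draw less.

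The primary analysis estimates event probabilities in order to plan later trials. Loss that is equal in both arms would still lower each arm's rate, in the reassuring direction.

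**Working it through.** **1. The passages side by side**

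| Place | What it implies about collection |
|---|---|
| 12.1, call description | Causal: effects of the treatment |
| 12.1, schedule row | Neutral |
| 3.0, 19.1, SAE and Grade 3-4 endpoints | No relatedness condition |
| 21.2, blinded reviewer | Disease-related events must be in the data, since the reviewer separates them from drug-related ones |
| 21.4, route | The calls, referring back to the earlier description |
| 12.4, EMR | Baseline health and the COVID illness only |

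The first row does not fit the next three. The text supplied contains no definition of an adverse event, no neutral question, and no instruction to record events whatever their cause, so nothing resolves the conflict.

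**2. Which events depend on the call alone**

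- COVID hospitalization and death: the EMR is a source that does not depend on the subject's view of cause.
- Non-COVID SAEs: outside the EMR scope in 12.4, so the call is the only stated source. The same holds for the non-COVID part of the any-reason hospitalization outcome in 19.1.
- Grade 3-4 events without hospitalization: the call is the only source stated for the endpoint. The daily questionnaire rates COVID symptoms, but no text links it to adverse event recording or grading.

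**3. The plan's own precision figure**

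30 subjects at 2:1 gives 30 × 2/3 = 20 on melatonin. The maximum standard error is √(0.5 × 0.5 / 20) = 0.112, or 11.2 percentage points. Section 19.2 states at most 11, which agrees after rounding.

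**4. Illustration of scale**

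The documents give no capture fraction, so everything here except n = 20 is assumed. Let p be the true event rate, h the share of events found through the EMR, and c the share of the remainder that the calls capture. Then

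observed rate = p × [h + (1 − h) × c].

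I take p = 20%, borrowed from the hospitalization rate anticipated in 21.1 purely as a scale. It is not a forecast of the events at risk, because COVID hospitalizations are the events with an EMR source.

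| h | c | Overall capture | Observed rate | Expected events in 20 |
|---|---|---|---|---|
| 0 | 0.9 | 0.90 | 18% | 3.6 |
| 0 | 0.75 | 0.75 | 15% | 3.0 |
| 0 | 0.5 | 0.50 | 10% | 2.0 |
| 0.5 | 0.5 | 0.75 | 15% | 3.0 |
| 0.8 | 0.5 | 0.90 | 18% | 3.6 |
| 1 | any | 1.00 | 20% | 4.0 |

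Clopper-Pearson 95% intervals, the method in 19.1: 4/20 gives 5.7% to 43.7%; 2/20 gives 1.2% to 31.7%.

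With c between 0.5 and 1, the downward shift runs from 0 to 10 points. The largest is 10/11.2 = 0.9 of the maximum standard error. A lower c would give a larger shift.

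**The case against.** The strongest reply is that this is loose wording and nothing more.

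- The bullet is a task summary addressed to participants; the next one tells the subject to let a courier come to the house. It is not the question asked on the call. That question would be on the follow-up data collection form, which 12.3 lists but the text does not reproduce.
- The protocol uses effect and event interchangeably: sections 3.0 and 21.3 name the special-interest items with different words.
- Section 12.2 answers what data are collected by pointing to the table, whose row is neutral. The days in 21.5 match that row; the bullet omits Day 1.
- The reviewer's remit and the any-reason hospitalization analysis make sense only if disease events are collected.

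Much of this stands. It makes all-cause intent likely, although that intent is inferred from a missing qualifier and is never stated. It therefore rules out a stronger reading that a reader might infer: that events are being filtered at source and that the endpoints are understated. The documents show a conflict and a risk, and do not show what staff ask.

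A second inference would be that the loss differs by arm, for example because drowsiness reveals the assignment and changes what subjects report. The trial is double-blind, and nothing in the documents describes such unblinding or differential reporting.

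The reply does not remove the conflict. Section 21.4 still points to the calls, staff could follow either description, and the EMR scope in 12.4 leaves part of the endpoints without a second source.

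**Conclusion.** The point holds as an inconsistency that puts complete capture of two primary safety endpoints at risk. The exposed events are mainly Grade 3-4 events without hospitalization and non-COVID SAEs.

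The loss cannot be sized from the documents. It is zero if the follow-up form already asks neutrally or if staff work from the schedule row. The 10-point shift above requires a 20% true rate, half of the events captured and no EMR recovery, all of which are assumed; if 80% of events were found in the EMR, the same half-capture would cost 2 points. Any loss would lower the recorded rates, and no between-arm bias is demonstrated.

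The change should be made because it decides what is collected in a trial whose primary purpose is safety, and it is cheap.

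**What to change.** 1. In 12.1, replace the causal phrase with an instruction that at each call the coordinator asks an open question about any health problem since the last contact, and records every adverse event whatever its suspected cause. The special-interest items are asked about alongside.
2. Use *adverse event* consistently in 12.1 and 21.3.
3. Check the follow-up form against this wording and align it if needed.
4. Keep drug-or-disease attribution with the blinded reviewer, as 21.2 already provides.
5. Extend the existing EMR review in 12.4 to SAEs of any cause, so that non-COVID SAEs and any-reason hospitalizations have a source besides the calls.

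The cost is a few sentences of protocol text, possibly a revised form, slightly longer calls, a somewhat wider record review, and a few more events for the existing reviewer to adjudicate.
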